
SCHEMA

Effect of Cannabis Administration and Endocannabinoids on HIV Neuropathic Pain

DESIGN: Our objective is to assess PLWH who have neuropathic pain and are currently using cannabis, including light use (1-4 times per month) and heavy use (5+ times per month). These participants will be enrolled in a study that consists of two stages: Stage 1) PLWH will participate in a 6-month mHealth text messaging program (Individual Monitoring of Pain and Cannabis Taken, or IMPACT) that will examine the association between cannabis obtained from local dispensaries and changes in daily pain. Participants will return for a visit after 6 months for follow-up testing so we can examine longitudinal changes in neuropathic pain, neuropsychological performance and EC function. Stage 2) A double blind crossover study where we administer three different doses of vaporized cannabis to each participant that contain THC and varying concentrations of CBD (low, medium, high), including: a) 2 vials of 0.01% CBD + 1.9% THC, b) 1 vial of 0.01% CBD + 1.9% THC and 1 vial of 5.1% CBD + 1.4% THC, and c) 2 vials of 5.1% CBD + 1.4% THC. Here we will examine the acute effects of cannabis obtained from NIDA on pain intensity, blood endocannabinoid (EC) levels, and the relationship of pain with heart rate variability (HRV).

POPULATION: PLWH with neuropathic pain and current cannabis use.

STRATIFICATION: none

REGIMEN OR INTERVENTION

Three doses of cannabis (with varying concentrations of CBD) administered once per day on three separate days.

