1.1 Background

HIV-related neuropathic pain (HIV-NP) represents a significant problem for PLWH. HIV sensory neuropathy (HIV-SN), typically characterized by sensory deficits, numbness, tingling, or pain in feet or hands, is a common health concern in people living with HIV (PLWH)¹. HIV-SN is often associated with neuropathic pain (NP) described as “stabbing”, “burning” or “aching” that is the most frequent source of HIV-SN disability², while the prevalence of reported pain in PLWH ranges from 27 to 97%³. A large scale study by our group indicated that 57% (881 out of 1539 PLWH) exhibited HIV-SN and 38% reported HIV-NP⁴. Treatment of HIV-NP remains difficult; a 2010 review indicated that only capsaicin, human nerve growth factor, and smoked cannabis showed superior pain reduction compared to placebo⁵. Studies at the University of California Center for Medicinal Cannabis Research (CMCR) indicate that 34-40% of patients exposed to cannabis cigarettes with delta-9-tetrahydrocannabinol (THC) exhibited significant pain reduction compared to 17-20% on placebo⁶⁻⁸. While THC doses in the 1.3% to 3.5% range alleviate pain for some participants, higher doses of THC (7-8%) did not provide additional benefit for pain reduction⁸ or actually increased capsaicin-induced pain in healthy volunteers⁹. Importantly, combined cannabidiol (CBD)/THC extracts are reported to be more effective at treating pain compared to THC alone in human cancer-related pain and in rodents^{10, 11}. CBD exhibits antioxidant and neuroprotective properties, inhibiting the release of inflammatory cytokines such as TNF α ¹². However, the optimal THC/CBD ratio for effective pain treatment is not yet known. There may also be discrepancies between data obtained from controlled clinical trials and the use of unregulated cannabis obtained from dispensaries. There is thus a clear need to close the gap between existing clinical data and real-life cannabis use from public sources, including the effects on the endocannabinoid (EC) system and NP.

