
time point. All response observations, including information from subjects who do not complete all experimental sessions, will be included in the analyses. Similar mixed-model analyses will be performed on the primary pain outcome after adjustment for psychomimetic side effects (measured with the ARCI scale) to assess for effects of the study drug on pain independent of subjective responses. The proportion of subjects with a 30% pain reduction, a standard for effective pain reduction⁶⁰ will be compared between each of the doses with chi-square tests; we will also calculate the number needed to treat (NNT) for a 30% pain reduction rate. We will also conduct analyses to examine the association between pain and EC biomarkers, including AEA, 2-AG, FAAH, and MAGL expression. A 5% significance level will be used for all testing. The association of pain levels with HRV will use a linear mixed-effects model, adjusting for potential confounders as above. Within-subject correlation will be accounted for using subject-specific random intercepts and slopes.

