7.2 Aim 2 Measures and Analyses

Based on our existing data for PLWH SMS compliance, we anticipate that participants will respond to 80-90% of the daily text messages during IMPACT. To address the issue of missing data, we will incorporate questions that allow participants to indicate their pain and cannabis use for the prior day if they did not respond to the earlier message. For days that have completely missing data, we will treat the intermittently missing data as missing completely at random. However, this assumption will be checked in sensitivity analyses by comparing the outcomes of participants based on the amount of missing data. Study dropout will be examined separately using statistical methods in current use [Diggle, Heagerty, Liang, and Zeger, *Analysis of Longitudinal Data*, 2nd ed., Oxford University Press, 2013]: The relationship between CBD, THC, and the CBD/THC ratio during a cannabis exposure event to changes in pain before and after the event will be examined using longitudinal data methods – e.g., mixed-effects linear models, controlling for potential confounders including baseline pain, in addition to those listed under Aim 1. The total CBD and THC consumed during the exposure will be calculated using the SUI method, estimating total grams of cannabis consumed multiplied by the percentages of CBD and THC content. Subject-specific random intercepts will be included in the model in order to account for the within-subject correlation of the outcome. Exploratory analyses will examine if there are different effects of reported cannabis strain (Sativa, Indica), individual types (e.g., OG Kush, Sour Lemon, etc.), or mode (smoking, vaporizing, ingesting food product) on pre-post changes in NP. We will also conduct exploratory analyses to examine if there is an interaction between reported levels of THC (low, < 1%, medium, 1-6%, high, > 10%) and CBD (low, < 1%, medium, 1-6%, high, > 10%) on pain change after drug use. The association of daily measures of pain levels with HRV will use a linear mixed-effects model, adjusting for potential confounders. The within-subject correlation will be accounted for using subject-specific random intercepts. Longitudinal changes in HRV between the first and last week will be assessed with a linear model that includes cannabis use (light vs. heavy) and CBD/THC intake, as predictors. Regression analyses will also examine the association between HRV and self-report pain measures quantified at the baseline and final visits.

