7.3 Aim 3 Measures and Analyses

We will use a linear model to examine the association between the total CBD, THC, and CBD/THC ratio during IMPACT and the change in NP, disease markers (CD4, viral load, Total Neuropathy Score, and neurocognitive global T-score), and EC biomarkers (AEA, 2-AG, FAAH, MAGL, CB2) from baseline to the final visit after month 6. We will control for confounders as in Aims 1 and 2, including any CBD and THC levels recorded at the baseline and final sessions. Linear models will compare the month 6 – baseline change in pain and in EC biomarkers between the heavy- and light-cannabis groups. One exploratory analysis will test for an interaction between group (light vs. heavy) and CBD and THC levels on change in NP and EC biomarkers. We will assess if exposure mode (smoking/vaporizing/ingestion) predicts pain outcome. We will examine if there is an association between pain change over time and changes in EC biomarkers. During the 6-month IMPACT, alterations may occur in cannabis use or pain medication (e.g., a person enrolled as a light cannabis user may start to engage in heavy use or begin using non-cannabis medication for pain, i.e., an opiate, which we will record with IMPACT). To address these issues we will conduct light vs. heavy use analyses based both on the baseline group classification and the actual use during IMPACT, include a cannabis use 'change' factor in the analyses (going from light to heavy use, or vice versa), and include the initiation of any non-cannabis pain medication as a factor in the model.

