For Aim 2, with 20% attrition over the 6 months of IMPACT we have $n= 80$ participants with 6 months (26 weeks) of data. We conservatively ignore the drop-out participants (who nonetheless contribute partial data). Assume, conservatively, that participants will use cannabis on average 2 times/week. This gives $n=80$ and $k=52$ observations/participant. If ICC is the intra-class, or within-participant correlation, the effective sample size (number of equivalent independent observations) is $n_{\text{eff}} = n/(ICC+(1-ICC)/k) \approx n/ICC$ [e.g., Killip, Mahfoud, Pearce, Ann Fam Med, 2004; 2:204-208.]. Assuming conservatively $\rho=0.5$ (or lower), we get $n_{\text{eff}} = 2n = 200$ [$n_{\text{eff}} = 160$]. We have 80% power to detect a (partial) correlation R between the individual predictors (Hypothesis 1: CBD, THC, and the CBD/THC ratio; Hypothesis 2: pain levels and HRV) and change in pain of $R = 0.218$ (or semi-partial $R^2 = 0.0475$), after adjusting for confounders. Calculations used G*Power.

For Aim 3, assuming $n = 80$ participants complete the 6-month follow-up, we have 80% power to detect an association between an individual predictor and response (e.g., total CBD and changes in neuropathic pain levels) of $R = 0.302$ (or semi-partial $R^2 = 0.092$), after adjusting for confounders. The calculations used G*Power.

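### The main Aim 2 analysis of event THC is planned and sized as a linear association, although the plan's own background describes a plateau; prespecify a THC term that can bend

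*Combined protocol and SAP*

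**What the plan says.** Section 1.1 gives the plan's own picture of THC dose and pain: relief for some participants at 1.3% to 3.5%, while "higher doses of THC (7-8%) did not provide additional benefit for pain reduction". It adds that pain rose at higher doses in one setting, capsaicin-induced pain in healthy volunteers.

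Section 7.2 sets the main Aim 2 analysis. "The relationship between CBD, THC, and the CBD/THC ratio during a cannabis exposure event to changes in pain before and after the event" is to be examined with longitudinal methods, and mixed-effects linear models are the example given. The exposure is an amount: grams consumed times percent content. Section 7.4 sizes this as "80% power to detect a (partial) correlation R between the individual predictors" and change in pain, with R = 0.218. Section 2.0 lists Aim 2 among the primary outcome measures.

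Three other provisions come close but do not supply a curved THC term:
- The quadratic in 7.1 is for time after dosing.
- The nonlinear fallback in 7.2 is for the CBD/THC ratio in the laboratory-versus-dispensary comparison.
- The THC bands in 7.2 (below 1%, 1-6%, above 10%) are exploratory, are aimed at a THC-by-CBD interaction, and leave 6-10% in no band.

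**The concern.** A single slope in raw dose suits a response that keeps rising. If relief rises and then levels off, the line averages the rising part with the flat part, and its expected slope shrinks as more events fall on the flat part. The plan's top band is above 10% THC, so it allows for products stronger than the 7-8% at which its background reports no added benefit. The gap in the bands, 6-10%, contains that same 7-8%.

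At stake is how the THC result of Aim 2 is read. A slope near zero could be reported as no association between THC and pain change, when the pattern in section 1.1 would produce such a slope from products that do relieve pain. Section 7.2 says that its comparison of laboratory and dispensary cannabis should inform policy recommendations, so the wording of Aim 2 conclusions matters.

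**Working it through.** **Inputs from the plan.** Alpha: "A 5% significance level will be used for all testing" (sidedness is not stated; the 1-df F test used here, equivalent to a two-sided test, reproduces the plan's figure). Sample: "with 20% attrition over the 6 months of IMPACT we have $n= 80$ participants". Events: "This gives $n=80$ and $k=52$ observations/participant". ICC 0.5. Detectable R = 0.218, R² = 0.0475.

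**Effective sample size.** n_eff = 80 / (0.5 + 0.5/52) = 157; the plan's approximation n/ICC gives 80/0.5 = 160. Section 7.4 prints both 200 and 160.

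**Reproducing the plan's figure.** Noncentral F with 1 and 158 df and λ = n_eff·R²/(1 − R²). With n_eff = 160, 80% power needs R = 0.2175, and R = 0.218 gives 80.2%. With n_eff = 200 the detectable R would be 0.195. The stated R therefore rests on 160 and on a 1-df term.

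**Assumptions for the check.** Relief rises linearly to 3.5% THC and is then flat. The whole curve explains the planned R² = 0.0475. Grams per use are equal, so potency stands for amount. Potency is uniform over the range shown. The documents give none of these, so several ranges are used.

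**Raw-dose line.** The line sees R_line = 0.218 × corr(dose, curve). For 0.5-15%, with x the potency and g = min(x, 3.5):
- Share of events below 3.5%: 3/14.5 = 0.207
- E[g] = 0.207 × 2 + 0.793 × 3.5 = 3.190
- Var(g) = 10.698 − 3.190² = 0.524; Var(x) = 14.5²/12 = 17.52
- Cov = 26.660 − 7.75 × 3.190 = 1.940
- corr = 1.940 / √(0.524 × 17.52) = 0.640
- R_line = 0.218 × 0.640 = 0.140; λ = 160 × 0.0195/0.9805 = 3.18; power 42%

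**Log-dose alternatives.** A 1-df line in log dose and a 3-knot restricted cubic spline in log dose (knots at the 10th, 50th and 90th percentiles, joint 2-df test) were fitted to the same curve by least squares. The share of curve variance captured multiplies 0.0475.

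| Potency range | corr | R_line | Raw line | Log line, 1 df | Log spline, 2 df |
|---|---|---|---|---|---|
| 0.5-6% | 0.917 | 0.200 | 73% | 78% | 68% |
| 0.5-10% | 0.762 | 0.166 | 56% | 73% | 69% |
| 0.5-15% | 0.640 | 0.140 | 42% | 67% | 69% |
| 0.5-25% | 0.506 | 0.110 | 29% | 58% | 64% |

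If every product is at or above 7%, g is constant. Every dose slope is then zero, and the test rejects only at its 5% level.

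**Where the plateau starts.** Section 1.1 does not say where between 3.5% and 7% relief levels off. With the plateau at 7%, the raw line has 80%, 77%, 67% and 50% for the same four ranges.

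**A mixed product range.** Assume 20% of events below 1%, 40% at 1-6% and 40% at 10-25%, with the plateau at 3.5%. The raw line has 45%, the log line 72%, and the spline 63-67% depending on how close to zero the weakest products lie.

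**Cost if the truth is exactly linear.** At R² = 0.0475 and n_eff = 160, a 1-df test has 80.2% and a joint 2-df test 70.8%.

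**The case against.** The strongest reply has four parts.

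1. Section 7.2 offers linear mixed models only as an example and fixes no functional form; a linear mixed model can hold a curved term, and bands are planned. This stands in part: it is too strong to say that the plan commits to a straight line. But 7.4 sizes one R per predictor, no curved THC term appears, and the bands are exploratory with a gap. An unstated form is itself a reason to state it.

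2. A flat slope correctly answers the association question, and the mean pre-post change can still be estimated. This stands. A reader might infer that Aim 2 cannot show any benefit of use; the documents do not support that. The mean change is uncontrolled, but it is there, and no section says that a flat slope will be read as no relief.

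3. Much of the gain comes from the log scale, not the spline. This stands: under the plateau at 3.5%, a 1-df log line does better than the spline for 0.5-6%, 0.5-10% and the mixed range. The spline is ahead for 0.5-15% and 0.5-25%. Its role is protection when the log shape is also wrong. Section 7.1 allows log transformation, but under Aim 1 and for normality.

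4. The overarching hypothesis concerns CBD and the CBD/THC ratio, and no potency distribution is given. Both are true. They limit the importance and the size of the point, but they do not remove it, because THC is a named Aim 2 predictor with its own stated power.

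**Conclusion.** The point holds for THC in the main Aim 2 analysis. Under a plateau at 3.5% with equal grams, the planned 80% for a raw-dose slope falls to about 73% if products stay within 0.5-6%, 42% for 0.5-15% and 29% for 0.5-25%. The loss is smaller if relief levels off later and negligible if nearly all products lie below the plateau. If nearly all lie on it, no dose term of any shape will show relief, and only the interpretive statement helps. All these sizes rest on assumed curves and potencies.

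Three wider readings are not supported:
- **Reversal.** A reader might infer that the background predicts a negative slope. The increase in pain in section 1.1 is confined to capsaicin-induced pain in healthy volunteers; for pain reduction it reports only no added benefit.
- **Aim 3.** Section 7.3 says "We will use a linear model to examine the association between the total CBD, THC, and CBD/THC ratio during IMPACT", which looks like the same problem. Those six-month totals mix frequency of use with dose per use, while section 1.1 concerns THC strength, and 7.3 also compares heavy with light users.
- **CBD.** Section 1.1 gives no evidence of a plateau for CBD.

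**What to change.** In section 7.2:
- Enter event THC amount (grams times percent) on a log scale, with a stated offset for zero-THC products, plus one curvature term from a 3-knot restricted cubic spline. Fix the knots and the offset in advance, since the mixed-range result above depends on the weakest products.
- Report the joint 2-df test and the fitted curve beside the linear slope, and name in advance which test carries the THC conclusion.
- State that a null or negative linear slope alone is not evidence of no relief.
- Make the exploratory THC bands contiguous so that 6-10% is covered.

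In section 7.4, give the power of the joint test at the same R and n_eff.

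The change is wording and a little extra analysis on data already being collected. It costs about 71% instead of 80% power if the truth is exactly linear, and a small loss (68% against 73% in the case above) if products stay at or below 6%.

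A comparison of use days with no-use days could be added as an exploratory analysis, but no more than that. No-use days have no pre-post pair, so a separate outcome must be defined, and pain itself prompts use.

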2.0 STUDY DESIGN

Our objective is to assess 100 community-dwelling PLWH with neuropathic pain (PLWH-NP) who are recruited and tested at the HIV Neurobehavioral Research Program (HNRP)/Center for Medicinal Cannabis Research (CMCR) facilities located at the UCSD Medical Center. These participants will be enrolled in a study that consists of two stages: 1) administration of three different doses of vaporized cannabis obtained from NIDA (one dose per day on three separate days) that contain THC and varying concentrations of CBD, including: a) 2 vials of 0.01% CBD + 1.9% THC, b) 1 vial of 0.01% CBD + 1.9% THC and 1 vial of 5.1% CBD + 1.4% THC, and c) 2 vials of 5.1% CBD + 1.4% THC; 2) participation in a 6-month text message monitoring study, the Individual Monitoring of Pain and Cannabis Taken (IMPACT), where pain and cannabis use from local dispensaries is tracked. We will use a randomized crossover design where all participants receive each of the three cannabis doses at the HNRP and then are subsequently enrolled into IMPACT. We will recruit individuals who are currently using cannabis at least once a month to treat pain. The primary outcome measures of the study will examine: 1) the acute effects of NIDA-obtained cannabis on pain, EC levels, and the relationship with HRV (Aim 1); 2) the association between dispensary-obtained cannabis and changes in pain reported via IMPACT (Aim 2); 3) the effect of chronic THC and CBD exposure on longitudinal changes in pain, EC measures, and neurocognitive performance (Aim 3). Secondary and exploratory analyses will compare NIDA-obtained and dispensary-obtained cannabis effects on neuropathic pain and evaluate if there are different effects of reported cannabis strain (Sativa, Indica), specific cannabis products (e.g., OG Kush, Sour Lemon, etc.), or mode (smoking, vaporizing, ingesting food product) on pre-post drug exposure changes in pain

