7.0 STATISTICAL ANALYSIS PLAN

7.1 Aim 1 Measures and Analyses

Data will be assessed for normality and transformations applied as needed (e.g., log). Neuropathic pain before and after acute cannabis administration will be assessed by NPRS and the von Frey test. Plasma AEA and 2-AG will be measured with LC/MS. Flow cytometry will quantify the percentage of PBMC that express CB2, FAAH, and MAGL, including monocytes, CD4+ T-cells, and CD8+ T-cells. To examine the effect of different CBD/THC products on NP and EC biomarkers, we will use a linear mixed model with subjects treated as a random effect to model the response measures. This methodology takes into account the repeated measures aspect of the within-subjects crossover study design, incorporating information from observations for each subject at different treatment doses and multiple time points within each dose. For initial modeling, terms will include dose (0.01%, 5.1% - 4 puffs, and 5.1% - 8 puffs) CBD treated as a categorical variable), time (0, 60, 120 and 180 minutes after exposure treated as a continuous variable), and dose x time interaction. Additional terms will also be included for the sequence in which the treatments were administered (e.g., low CBD vs. medium CBD) and for second-order time (time²). The quadratic term is intended to model a U-shaped response curve if responses initially increase (or decrease), reach a maximum (or minimum), then decrease (or increase) back to baseline levels. For each outcome measure, each of these last 2 terms will be omitted from subsequent models and not reported if nonsignificant. Any potential factors that associate with outcome variables at the $\alpha = 0.20$ level in single-predictor analyses (history of light vs. heavy cannabis use, mode of prior cannabis use – i.e., engaging in smoking, or vaporizing, or both), time since last cannabis use before baseline, duration of cannabis use over lifetime, presence of adolescent cannabis use, duration of HIV infection, nadir CD4, viral load, gender, the presence of other non-cannabis analgesic medications, history of non-cannabis substance use disorders) will be included in the linear model. Dose effects at each time point will be assessed with mixed modeling after re-coding time as a categorical factor and including dose and dose x time terms (plus a term for sequence if this is significant in the initial model). Differences among doses will be evaluated using the Tukey honestly significant difference (HSD) comparison tests for differences of effects over all time points and contrasts within each

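### The prior-mode confounder in 7.1 leaves out ingestion, so adjustment for mode is incomplete where it is used, mainly in Aims 2 and 3, and ingest-only users have no stated level

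*Combined protocol and SAP*

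**What the plan says.** Three places in the combined protocol and SAP treat ingestion as a mode of use:

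- Section 2.0, secondary and exploratory analyses: "or mode (smoking, vaporizing, ingesting food product) on pre-post drug exposure changes in pain".
- Section 7.2, exploratory analyses: "or mode (smoking, vaporizing, ingesting food product) on pre-post changes in NP".
- Section 7.3: "We will assess if exposure mode (smoking/vaporizing/ingestion) predicts pain outcome".

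Section 7.1 lists candidate confounders that enter the linear model if they are associated with the outcome at alpha = 0.20 in single-predictor analyses. One of them is "mode of prior cannabis use – i.e., engaging in smoking, or vaporizing, or both".

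That list is reused. The Aim 2 models are described as "controlling for potential confounders including baseline pain, in addition to those listed under Aim 1", and 7.3 says "We will control for confounders as in Aims 1 and 2".

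Eligibility does not depend on route. Section 3.1.5 asks only for current use, and 2.0 adds use for pain at least monthly. Section 7.1 also commits to analysing every response, including those from people who miss sessions.

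**The concern.** The plan regards ingestion as a mode that may change the pain response, yet its mode confounder cannot record it. Two groups are affected. People who ingest as well as smoke or vaporize have a level, but their ingestion is invisible. People who only ingest have no stated level.

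The first problem matters most in Aims 2 and 3, where CBD and THC intake is observed rather than assigned and the comparisons are at least partly between persons. If people who ingest differ from others both in CBD/THC intake and in pain change, a mode term that cannot see ingestion leaves that difference in the estimated association.

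The second problem is one of handling. A missing covariate value usually removes the participant from a regression or mixed model. That loss would be selective, falling on people whose usual route differs from the vaporized laboratory doses.

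**Working it through.** **Step 1: what the wording can record.** The plan gives no coding, so two natural codings of the 7.1 wording are set beside a three-indicator version.

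| Prior use | Three levels | Two indicators (smokes, vaporizes) | Three indicators (smokes, vaporizes, ingests) |
|---|---|---|---|
| Smokes only | smoking | 1/0 | 1/0/0 |
| Smokes and ingests | smoking | 1/0 | 1/0/1 |
| Vaporizes only | vaporizing | 0/1 | 0/1/0 |
| Vaporizes and ingests | vaporizing | 0/1 | 0/1/1 |
| Smokes and vaporizes | both | 1/1 | 1/1/0 |
| All three | both | 1/1 | 1/1/1 |
| Ingests only | none: missing or forced | 0/0 | 0/0/1 |

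Both codings of the current wording merge mixed users with inhaled-only users. Only the three-level coding puts ingest-only users at risk of being dropped or misclassified; two indicators keep them as 0/0.

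**Step 2: where the covariate acts.** In 7.1 it enters a model only if it passes the alpha = 0.20 screen, and the screen itself uses the same coding. Sections 7.2 and 7.3 refer back to the Aim 1 list without saying whether the screen is repeated. Prior mode is constant within a person, and the Aim 1 dose comparisons are within-subject with a subject random effect. Miscoding a person-level main effect therefore has little influence on the dose contrasts.

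**Step 3: the plan's own figure.** Section 7.4 gives, for Aim 3, n = 80, 80% power and R = 0.302 (semi-partial R² = 0.092). Sidedness is not stated; a two-sided 5% test of one coefficient is assumed, with f² = R²/(1 − R²) and noncentrality √(n·f²). Solving for 80% power at n = 80 gives R = 0.302, R² = 0.091, so the stated figure reproduces.

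**Step 4: illustration if ingest-only users were dropped.** Their share is not in the documents, so it is assumed. With R = 0.302, f² = 0.0912/0.9088 = 0.1004. At n = 80 the noncentrality is √8.03 = 2.83; at n = 72 it is √7.23 = 2.69.

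| Assumed share dropped | n | Power at R = 0.302 | R detectable at 80% power |
|---|---|---|---|
| 0% | 80 | 79.9% | 0.302 |
| 5% | 76 | 77.8% | 0.310 |
| 10% | 72 | 75.5% | 0.317 |
| 20% | 64 | 70.4% | 0.335 |
| 30% | 56 | 64.4% | 0.356 |

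For Aim 2, an effective sample size of 160 reproduces the stated R = 0.218. If that size fell in proportion to a 10% loss, to 144, power at R = 0.218 would go from 80.2% to 75.9%. For Aim 1, a 10% loss gives f = 0.180 × √(100/90) = 0.190, the figure 7.4 already gives for 90% completion.

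**Step 5: cost of a fuller covariate.** Three levels or two indicators use two degrees of freedom; three indicators use three. At n = 80 the detectable R is 0.302 with one predictor and 0.303 with ten, so the extra term has almost no effect on power.

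**The case against.** A reader might infer that ingest-only users will drop out of the adjusted models in all three aims. The documents do not support that. No coding is specified, two indicators would keep these users in, the term must first pass a screen in 7.1, and the commitment to use all responses can be read as an instruction not to drop anyone. Nor do the documents support inferring that the Aim 1 dose effects would be wrong (Step 2), or that the plan ignores ingestion altogether: the exploratory mode analysis in 7.2 and the exposure-mode analysis in 7.3 include it.

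Three further arguments deserve a hearing.

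- The plan uses i.e. loosely elsewhere, for instance where 7.3 names an opiate as a non-cannabis pain medication, so the 7.1 list might be only examples. But that list ends with a combination of its two members, which reads as complete.
- Every laboratory dose is vaporized, so experience of inhaling may be the intended confounder. That is a fair reason in Aim 1. It does not carry over to Aims 2 and 3, where participants use dispensary products by any route.
- Prior mode is history, whereas the other sections concern the route of current exposure. A participant who now only ingests but once inhaled may have a level. This stands: no reference period is given, and the group without a level may be small. The exclusion of some respiratory conditions in 3.2.5 could make it smaller still.

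What remains is that ingestion cannot be recorded under either natural coding of the wording.

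**Conclusion.** The inconsistency is in the text, and it is minor. Where the prior-mode covariate is used, users who both ingest and inhale are coded as inhaled-only, and ingest-only users have no stated level. The main consequence is incomplete adjustment for mode in the between-person analyses of Aims 2 and 3. The size of any resulting bias cannot be calculated from the documents. Dropping ingest-only users is a possibility that depends on the coding, and it would conflict with the commitment in 7.1. If it happened to an assumed 10%, Aim 3 power would be about 76% instead of 80%; that figure is an illustration and rests on the assumed share, on complete-case analysis and on a two-sided test.

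**What to change.** In 7.1, define prior mode by three yes/no indicators (smokes, vaporizes, ingests), and use the same three wherever 7.2 and 7.3 carry the Aim 1 confounder list forward. Confirm that the planned substance-use assessment records route: section 4.3 says that substance use is assessed at the pre-entry and final visits but not that route is captured. The cost is a wording change and about one extra model degree of freedom, plus one item on the assessment form if route is not already asked.
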